9.7 Data analysis

Procedures

We will use a matched cohort design to evaluate the effectiveness of seasonal influenza vaccine in comparison with not receiving a seasonal influenza vaccine. Individuals who have received the vaccine will be matched on the day of vaccination with individuals who have not yet received the vaccine. Individuals will be matched on age (5-year bins), sex, region of residence, and selected comorbidities. The day the seasonal vaccine dose was administered within each matched pair will serve as the index date for both individuals. If individuals who were included as a matched non-vaccinated individual

(i.e., a reference individual) receive a vaccine later than the assigned index date, the pair will be right-censored on the day the non-vaccinated individual is vaccinated. In these cases, the non-vaccinated individuals will be allowed to potentially re-enter as vaccine recipients in a new matched pair on that given date.

Statistical analysis

We will follow individuals from day 14 after the index date (to ensure full immunisation) up until the day of an outcome event, death, emigration, or end of the study, whichever occurs first. Additionally, we will censor individuals with a positive PCR test for influenza in our follow-up period 14 and 30 days after the test (as a positive test will be part of the outcome definitions) for the influenza hospitalisation and death outcome analyses, respectively. We will right-censor matched pairs when the reference unvaccinated individual receives a vaccine during follow-up. Cumulative incidences will be estimated by the Aalen-Johansen estimator, and from these we will calculate the comparative VE as $1 - \text{risk ratio}$ at the start of week 18 (depending on data availability) since index date. The corresponding 95% CI will be calculated using the delta method. Country-specific estimates will be combined by random-effects meta-analyses implemented using the *mixmeta* package in R.

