$$PERR = \frac{\frac{Event\ Rate_{Vaccinated,current}}{Event\ Rate_{Vaccinated,pre-vaccinated}}}{\frac{Event\ Rate_{Unvaccinated,current}}{Event\ Rate_{Unvaccinated,pre-vaccinated}}}$$

This ratio-of-ratios approach aims to adjust for pre-existing differences between those who choose vaccination and those who do not.

We will use Poisson regression to estimate event rates during the pre-vaccination and current periods. We will report point estimates and 95% confidence intervals for the PERR-adjusted measure of VE (1-PERR). The precision of these estimates will depend on the number of events in the pre-vaccination period. With high vaccine uptake and the vaccination occurring early in the start of the influenza season, the pre-vaccination period may produce fewer events. PERR results will be interpreted carefully and considered alongside the main matched cohort analyses and other supplementary analysis.

Negative control outcomes (NCO)

To evaluate the possible residual confounding in analysis of influenza vaccine effectiveness, we will analyse the association between influenza vaccination and the following negative control outcomes (NCO) in our main study design: Lower back pain (ICD10: M543-M545), clavicle fracture (ICD10: S420), and diverticulitis (ICD: K57).

Analysing negative control outcomes is a way to assess residual confounding. (70) Negative control outcomes such as lower back pain, clavicle fracture, and diverticulitis are conditions biologically unrelated to both vaccination and influenza. Any association between influenza vaccination and these outcomes would suggest residual confounding e.g. by healthcare seeking behaviour which could bias VE estimates. If no associations are found, it supports the validity of the primary analysis. Significant associations would indicate confounding that requires further adjustment or caution in interpretation. This relies on the assumption that the association between influenza vaccination and the negative control outcome is subject to the same confounders as the association between influenza vaccination and the influenza outcomes. Including negative control outcomes strengthens the study's credibility.

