The study population will mirror the primary VE analysis, consisting of individuals aged 65 years or older, and adults under 65 years at high-risk. Vaccinated and unvaccinated individuals will be matched and the start of follow-up for matched pairs will be set at 14 days post-vaccination, ensuring alignment with the primary analysis. The statistical analysis will be conducted in the same way as our main cohort analysis, but negative control outcomes (lower back pain, clavicle fracture, and diverticulitis) will be evaluated instead of the influenza-related outcomes.

The results will be presented as cumulative incidence curves with RD and VE estimates. If no significant associations are found between influenza vaccination and the selected NCOs, this will support the validity of the primary VE analysis and suggest minimal residual confounding. If significant associations are observed, this will indicate residual confounding (e.g., differences in healthcare-seeking behavior) and warrant further exploration or caution in interpreting VE estimates.

Regression discontinuity analysis

For vaccination policies with treatment assignment according to age, regression discontinuity analyses (RDA) can be used to estimate a local average treatment effect (LATE) among individuals whose vaccination status is shifted by an eligibility threshold. Thus, we can estimate the LATE among 60-69-year-olds by comparing the risk in 65-69-yr-olds to the risk in the 60-64-yr-olds. This will provide a valid causal estimate under the assumptions of a) similar baseline risk of the influenza outcome in the two age groups, and b) strict adherence to the age recommendations. If adherence is not strict, we can

use fuzzy regression discontinuity analysis which uses an instrumental variables approach, where the cut-off is an instrument for actual treatment uptake. (52)

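### The negative control outcomes are read by statistical significance alone, so an imprecise null counts as reassurance and a trivial significant association counts as confounding

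*Protocol*

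**What the plan says.** Protocol section 9.8 (Negative control outcomes) names three outcomes: "Lower back pain (ICD10: M543-M545), clavicle fracture (ICD10: S420), and diverticulitis (ICD: K57"). On method it says "The statistical analysis will be conducted in the same way as our main cohort analysis". Section 9.7 describes that analysis: Aalen-Johansen cumulative incidences, a risk ratio with "The corresponding 95% CI will be calculated using the delta method", and random-effects meta-analysis over countries.

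The reading of the results is stated twice. The first time it is "If no associations are found, it supports the validity of the primary analysis". The second time significance is the explicit criterion: when none of the NCO associations is significant, "this will support the validity of the primary VE analysis and suggest minimal residual confounding". In the other direction, "If significant associations are observed, this will indicate residual confounding (e.g., differences in healthcare-seeking behavior"), and this calls for further exploration or caution.

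The one condition attached to the inference is that the NCO association is "subject to the same confounders as the association between influenza vaccination and the influenza outcomes". That is a condition on the choice of outcome and says nothing about precision.

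**The concern.** A non-significant result can mean that there is little confounding, or that there were too few events to see it. The rule does not separate the two. It attaches the phrase minimal residual confounding to both. The reverse reading has the matching weakness: with a common NCO and large numbers, a very small association becomes significant and is labelled confounding regardless of size.

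The protocol already handles this elsewhere in section 9.8. For the prior event rate ratio (PERR) analysis it promises to check that there are enough pre-vaccination events for stable estimates. For the regression discontinuity analysis it promises to look at outcome numbers with power in mind. The NCO section has no such check.

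The NCO analysis uses the main matched design in both target groups. The test-negative study is Danish only, PERR covers influenza hospitalisation, and the discontinuity analysis covers ages 60-69 and excludes high-risk people under 65. Section 8 says the findings are meant to inform regulatory decisions, so an over-confident statement about confounding would matter.

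**Working it through.** **Stated figure.** The protocol gives no event count, power or detectable bias for the NCOs, so there is nothing to reproduce. The calculation below shows what the rule does under stated assumptions.

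**Inputs from the protocol**
- 1:1 matching (Table 1).
- Follow-up from day 14 to week 18: 18 × 7 − 14 = 112 days. This is on the generous side, because pairs are censored when the control is vaccinated and section 9.7 reads the risk at the start of week 18.
- Two-sided 5% level, inferred from the 95% CI in section 9.7.
- A rough guide to the pairs aged 65+ that can be followed throughout, taken as the unvaccinated in section 9.5:
  - Denmark: 1.211 million × 24.4% = 295,484
  - Finland: 1.315 million × 39% = 512,850
  - Swedish regions: 280,000 × 31% = 86,800, using national coverage
  - Sum: 895,134

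**Assumed, not in the protocol:** NCO incidence of 50 (rare) or 500 (common) per 100,000 person-years, and a spurious risk ratio of 0.85.

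**Formulas**
- Events per arm: e = pairs × incidence × 112/365.25
- 95% CI when the observed RR is 1.00: exp(±1.96 × √(2/e)). Its lower end is also the significance limit.
- Power = Φ( −ln 0.85 / √(1/e + 1/(0.85e)) − 1.96 )

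**One line in full:** 300,000 × 0.0005 × 112/365.25 = 46.0 events. The standard error is √(1/46.0 + 1/39.1) = 0.2175. Then 0.1625/0.2175 − 1.96 = −1.21, so power is 11%.

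| Incidence per 100,000 | Pairs | Events per arm | CI at RR 1.00 | Power for RR 0.85 |
|---|---|---|---|---|
| 50 | 86,800 | 13 | 0.47-2.14 | 6% |
| 50 | 300,000 | 46 | 0.66-1.50 | 11% |
| 50 | 895,134 | 137 | 0.79-1.27 | 25% |
| 500 | 86,800 | 133 | 0.79-1.27 | 25% |
| 500 | 300,000 | 460 | 0.88-1.14 | 66% |
| 500 | 895,134 | 1,372 | 0.93-1.08 | 98% |

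The rows with 895,134 pairs simply add the countries and ignore between-country heterogeneity, so they are optimistic for a random-effects pooling.

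**All three NCOs together.** Take illustrative incidences of 50, 250 and 500 per 100,000 and independent outcomes. With 300,000 pairs the powers are 11%, 39% and 66%. At least one NCO flags the bias with probability 1 − 0.887 × 0.614 × 0.344 = 81%, so all three miss it 19% of the time. With 100,000 pairs the powers are 6%, 16% and 28%. The joint probability is then 43%, and all three miss it 57% of the time.

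**The other direction.** In the last row an observed RR of 0.93 is already at the significance limit. With 10,000 events in total the limit is about 0.96.

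**The case against.** The strongest reply is that the NCOs are one strand among several. Section 9.8 lists them with the test-negative study, PERR, regression discontinuity and testing frequency, and section 9.9 promises triangulation. The wording is hedged: a null supports and suggests. Risk ratios with 95% CIs, pooled over countries, already follow from sections 9.7 and 9.8, so a careful reader would see a wide interval. A numerical margin could reasonably be left to a statistical analysis plan, which is not at hand. All of this stands, and it limits the harm. None of it supplies a precision condition, and the protocol does not leave the interpretation open: it fixes it.

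Three stronger readings are tempting, and the documents do not support them.
- A reader might infer that a null NCO result automatically validates the VE estimates, or that the NCOs are the main confounding check. No VE result is accepted or rejected on an NCO test, and the protocol does not rank the supplementary analyses.
- A reader might infer that the NCO analysis is underpowered as a whole. Without event rates this cannot be shown, and a common NCO pooled over countries could be well powered.
- A reader might infer a false-alarm risk near 60%, from 1 − 0.95^18. That needs 3 outcomes × 3 countries × 2 trials, all independent and read separately. Pooled over countries there are 6 tests (26%), and 3 within one trial (14%). A positive result leads only to exploration or caution.

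**Conclusion.** The point holds as a fault in the interpretive rule. Significance is the sole criterion in both directions, with no regard to interval width or size of association. Under the assumed rates, power to flag an RR of 0.85 runs from about 11% (rare NCO, 300,000 pairs) or 25% (rare NCO, about 0.9 million pairs) to 98% (common NCO, about 0.9 million pairs). The consequence is over-reassurance from imprecise nulls, most likely for rare outcomes, single countries and other small strata, and it is partly offset by the other supplementary analyses. If a bias of 0.85 carried over fully to an influenza outcome, a true VE of 40% would appear as 1 − 0.60 × 0.85 = 49%. That transfer is an illustration and not something the protocol claims. The rule should be corrected, but the fault does not undermine the main design.

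**What to change.** In section 9.8, replace both statements of the rule with one based on size and precision:
- Report the event counts, risk ratio and 95% CI for each NCO, pooled and by country.
- State minimal residual confounding only when the CI excludes a bias that the investigators have specified as material before NCO results are seen.
- Call a null with a wider interval inconclusive.
- Read a significant but trivial association by its size.

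The investigators should choose the bound with the likely event counts in view. A margin of 0.90-1.11, for instance, could not be met with 460 events per arm even at an observed RR of exactly 1.00 (CI 0.88-1.14); it would take roughly 700 per arm. No particular margin is required. Nor is a correction of VE by the NCO ratio, since that would assume that confounding transfers one-for-one to the influenza outcomes.

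The cost is a few sentences and no new data. The downside is that some NCO checks, especially for rare outcomes or small strata, will be reported as inconclusive.

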ICU admission	Denmark	The National Patient Register and the Danish Microbiology Database. Defined as admission to an intensive care unit facility during hospitalization for influenza.
	Finland	Finnish Intensive Care Consortium's Quality Register for Intensive Care, National Care Register for Health Care and the National Infectious Diseases Register. Defined as admission to an intensive care unit facility during hospitalization for influenza.
	Sweden	The Swedish Patient Register, Quality Register for Intensive Care and the Register on surveillance of notifiable communicable diseases (SmiNet). Defined as admission to an intensive care unit facility during hospitalization for influenza.
All-cause mortality	Denmark	The Civil Registration Defined as a recording of death in the respective administrative demographic register (vital status is prospectively updated in these registers and also include information on the date of death).
	Finland	The Finnish Population Information System

		Defined as a recording of death in the respective administrative demographic register (vital status is prospectively updated in these registers and also include information on the date of death).
	Sweden	The Total Population Register, the Cause of Death Register Defined as a recording of death in the respective administrative demographic register (vital status is prospectively updated in these registers and also include information on the date of death).

Covariates

Determinants of vaccination and study outcomes are potential confounders in our studies. The richness of our health registers will allow us to provide detailed characterisations of health and disease status in individuals. We will be able to take the following confounders into account through exact matching: age (5-yr bins), sex, region of residency, and number of selected comorbidities (by 0, 1, 2, or ≥ 3 of chronic pulmonary disease, cardiovascular conditions, diabetes, autoimmunity-related conditions, cancer, and moderate-to-severe renal disease) as presented in Table 6.

Table 6. List of covariates

Variable	Country	Data source and details	Values/codes
Age	Denmark	The Civil Registration System. Recorded birth year. Age defined as 2024 minus birth year.	Categorical (for adjustment, using birth year): 5-year bins Binary (for stratification): $</\geq 75$ years

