While this method can yield robust causal insights under relatively few assumptions, it faces limitations related to sample size, adherence, and external validity. We will interpret RDA findings as part of our broader range of supplementary analyses, recognizing that they estimate a local average treatment effect for compliers in a narrow age interval that may not generalize to the whole population, and should be considered alongside the main cohort findings and other designs (e.g., TNCC, PERR). We will carefully evaluate the number of outcomes in this age range to ensure sufficient power. Even if RDA provides a rigorous causal estimate for the subset near 65, it may not reflect the effect in much older or younger individuals.

We will focus on individuals in an age band of 60-69 years, where the policy recommends seasonal influenza vaccination at age 65. We will extract data on vaccination status at the end of the study period or date of the outcome (yes/no), age (in years), and influenza-related hospitalizations for individuals aged 60-69. This subset ensures that the age threshold of 65 is central in the data, capturing individuals who are just below (60-64) and just above (65-69) the cutoff. Individuals below 65 who are at high-risk will be excluded since they were also offered vaccination. Influenza vaccination will be as assigned as the “treatment” variable. The “instrument” will be a binary indicator of whether an individual’s age is ≥ 65 (the vaccination policy cutoff). This instrument should, in theory, increase the probability of vaccination but is not assumed to directly affect health outcomes other than through vaccination.

The statistical analysis will be conducted using a fuzzy regression discontinuity model. The probability of being vaccinated can be estimated as a function of age relative to 65 (e.g., age - 65) and an indicator for crossing the 65-year threshold. The predicted probability of being vaccinated will then be used to estimate the effect on the outcome of interest (influenza-related hospitalisation). The package *rdrobust* in R can be used to conduct this analysis. We will also construct figures to visualize the discontinuity for outcome and for treatment.

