The main assumption is that, aside from the jump in vaccination likelihood at age 65, individuals just below vs. just above 65 should be comparable in terms of health and risk factors. To check this, we will inspect covariate distributions around the cut-off. We also expect to observe a noticeable “jump” in vaccination rates at age 65. If we do not observe this jump, it may indicate that the vaccination policy recommendation has weak influence, and the instrument’s strength may be inadequate.

Testing frequency

Tracking the frequency of influenza testing among vaccinated and unvaccinated individuals during follow-up provides insights into residual healthcare utilization or access bias. Testing rates can be compared between the groups to identify discrepancies that could influence VE estimates. We will assess testing frequency among vaccinated and unvaccinated individuals and stratify by calendar month to evaluate whether they are consistent across both groups and months, or driven by specific factors (e.g., timing patterns in a situation of increased testing activity during high influenza season). Ideally, we want the testing frequency to be similar. The results will be presented as the number of tests per group and calendar month, in a table or a graph. These steps ensure that any observed associations between vaccination and outcomes are not unduly influenced.

Sensitivity analysis before full immunization

We will conduct a sensitivity analysis using the primary cohort design (TTE approach) to evaluate vaccine effectiveness (VE) with an alternative time zero. The objective is to determine whether there is a difference in the incidence of influenza hospitalizations when time zero is set at the day of vaccination (Day 0) versus the day of full immunization (Day 14). Accordingly, we will estimate VE for the period from Day 0 to Day 14, and from Day 0 until the end of follow-up, to assess any potential effect of early events on our vaccine effectiveness estimates.

Quality control

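### The regression discontinuity analysis is described with two different estimands, and the 65-69 versus 60-64 contrast would bias effectiveness toward zero if hospitalisation risk rises with age

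*Protocol*

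**What the plan says.** All of this is in the Protocol. Section 9.8 (Regression discontinuity analysis) opens by saying that "we can estimate the LATE among 60-69-year-olds by comparing the risk in 65-69-yr-olds to the risk in the 60-64-yr-olds". It calls the result causally valid under two conditions: "similar baseline risk of the influenza outcome in the two age groups", and strict adherence to the age recommendation. If adherence is not strict, a fuzzy version can be used.

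Later in the same section the wording changes. "The statistical analysis will be conducted using a fuzzy regression discontinuity model". The scope becomes local: "Even if RDA provides a rigorous causal estimate for the subset near 65", it may not carry over to much older or younger people. The main assumption becomes that "individuals just below vs. just above 65 should be comparable in terms of health and risk factors".

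For the model, the probability of vaccination "can be estimated as a function of age relative to 65 (e.g., age - 65) and an indicator for crossing the 65-year threshold". For the outcome the text says only: "The predicted probability of being vaccinated will then be used to estimate the effect on the outcome of interest". The rdrobust package is offered as something that can be used. High-risk persons are excluded below 65; no matching exclusion is stated above 65.

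Section 9.3 lists age, in 5-year bins, among the confounders to be matched exactly. Table 6 gives the age variable: "Recorded birth year. Age defined as 2024 minus birth year".

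**The concern.** The section contains two estimands with two identifying assumptions. One is a contrast of two 5-year groups, offered as the effect among 60-69-year-olds, and it needs equal baseline risk across groups whose mean ages are 5 years apart. The other is the effect at the cut-off, which needs only that risk would run smoothly through 65. The text blurs them further by describing 60-64 as just below and 65-69 as just above the cut-off.

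Equal baseline risk is hard to defend in a protocol that matches on 5-year age bins because age is a confounder. If risk rises with age, the older group carries extra risk that has nothing to do with vaccination, and the contrast charges it against the vaccine. An outcome stage that used only the predicted vaccination probability would do the same. The analysis is one of several meant to show whether the cohort estimates are confounded, so a downward bias here could make a sound cohort estimate look doubtful.

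**Working it through.** The protocol gives no size or effect figure for this analysis, so there is none to reproduce. The check is a calculation of expected values, without sampling error.

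**Inputs.** Ages 60 to 69 in whole years, equal numbers at each age (assumed), so mean ages are 62 and 67. The documents give no age gradient and no coverage for 65-69 or for non-risk 60-64. The nearest figures are Danish coverage of 75.6% at 65+ and 29.2% in risk groups below 65 (section 9.5), and one cited effectiveness of 61.2% against hospitalisation (section 7). Assumed for the main example: true effectiveness VE = 50%, coverage 15% below and 65% above 65, gradient g of 3%, 5% or 7% per year.

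**Model.** Unvaccinated risk at age a, relative to age 65, is (1+g)^(a-65). Risk at age a is that value times (1 - VE x coverage).

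**Group contrast.** The vaccination effect is (mean risk 65-69 - mean risk 60-64) / (0.65 - 0.15). Dividing minus this effect by an unvaccinated risk gives VE. Two denominators are shown: the true unvaccinated risk at 65 (equal to 1), and the unvaccinated risk implied by the contrast itself.

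At g = 5%:
- Mean unvaccinated risk is 0.8659 at 60-64 and 1.1051 at 65-69.
- Risk at 60-64 is 0.8659 x (1 - 0.5 x 0.15) = 0.8010. Risk at 65-69 is 1.1051 x (1 - 0.5 x 0.65) = 0.7460.
- Effect = (0.7460 - 0.8010)/0.5 = -0.110.
- VE = 0.110/1 = 11.0%. With the implied denominator 0.8010 + 0.15 x 0.110 = 0.8175, VE = 13.5%.

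| g per year | Risk 60-64 | Risk 65-69 | VE, risk at 65 as denominator | VE, implied denominator |
|---|---|---|---|---|
| 0% | 0.9250 | 0.6750 | 50.0% | 50.0% |
| 3% | 0.8472 | 0.7167 | 26.1% | 29.5% |
| 5% | 0.8010 | 0.7460 | 11.0% | 13.5% |
| 7% | 0.7585 | 0.7763 | -3.6% | -4.7% |

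**Two-stage fit, age in the vaccination stage only.** With coverage flat on each side, this gives the same values as the group contrast. If coverage rises 1 point per year of age within each side, it gives 25.5%, 9.9% and -5.0% (risk at 65 as denominator).

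**Age in both stages.** With flat coverage and the same denominator, a common linear age term gives 49.2%, 48.7% and 48.3%. Separate slopes on each side give 49.6%, 49.0% and 48.1%.

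**When does the group contrast reach zero?** Setting the two risks equal gives g = [(1 - c0 x VE)/(1 - c1 x VE)]^(1/5) - 1, where c0 and c1 are coverage below and above 65.
- Main example: (0.925/0.675)^(1/5) - 1 = 6.5% per year.
- Over VE 30-61.2%, c0 5-29.2% and c1 50-75.6%: from 1.4% to 12.5% per year.
- With c0 5%, c1 75.6% and VE 61.2%, there is no reversal up to g = 10%; the estimate is then 11.2%.

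**The one-sided exclusion.** Suppose 20% of those above 65 are high-risk with twice the risk of others. Baseline risk then jumps at 65 by 1 + 0.2 x (2 - 1) = 1.2. With g = 5%, coverage 15%/60% and true VE 40%, age in both stages gives 6.2% (common slope) or 5.2% (separate slopes). With three times the risk, the jump is 1.4 and the results are -26.5% and -28.5%. These inputs are also assumed.

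**The case against.** The best defence is that the group comparison is introductory. It is phrased as something that can be done, its conditions are stated, and the section moves to the fuzzy design when adherence is not strict, which is the case in every example above. The binding sentence commits to fuzzy regression discontinuity. That stands, but the opening still names a different population and a different assumption, and nothing later withdraws them.

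Four stronger readings are tempting and are not supported.
- A reader might infer that the planned model omits age from the outcome stage. The text is silent; it does not exclude age. The fuzzy design, the named package and the planned plots of the discontinuity in the outcome all suggest that age would be modelled, and an analysis plan not at hand could settle it. This half is an ambiguity.
- A reader might infer that the vaccine effect will cancel or reverse. That depends on the gradient, the coverage jump and the true effectiveness, none of which the protocol gives for this age band.
- A reader might infer that the result would overturn the cohort estimate. No rule lets it. The analysis is read beside the cohort, test-negative and prior-event-rate results, with its limits stated and with checks of covariates and of the uptake jump at the cut-off.
- A reader might blame whole-year age for the bias. The check uses whole years throughout and still recovers 48-50% once age is in both stages.

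**Conclusion.** The concern holds as an inconsistency in estimand and identifying assumption, with an outcome stage left open. The direction of bias is firm: under the group contrast, or a second stage on predicted vaccination alone, any positive age gradient moves an effective vaccine's estimate toward zero. The size is conditional. For a true 50% and coverage 15%/65%, about 26-29%, 11-14% and -4 to -5% would be seen at 3%, 5% and 7% per year, depending on the denominator. Recovery to 48-50% with age in both stages assumes no other jump in risk at 65, and the exclusion of high-risk persons on one side only works against that assumption. Severity is low to moderate, because the analysis is supplementary.

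**What to change.** In Protocol section 9.8:
- Delete the 65-69 versus 60-64 comparison and the assumption of similar baseline risk in the two groups.
- Define one estimand: the effect at age 65 among those whose vaccination is shifted by the threshold.
- State that age minus 65 enters both the vaccination and the outcome stage, with separate slopes on each side.
- In the same edit, reconcile the exclusion of high-risk persons, so that the populations on the two sides of 65 are defined alike. Age terms do not remove the jump that the present rule creates.

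Optionally, build the running variable from date of birth where Table 7 shows that the register holds it (Denmark and Finland).

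The cost is a few sentences and a few lines of code. The interval will be wider than for the simple group contrast.

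### The regression discontinuity analysis drops high-risk people only below age 65, so baseline risk jumps at the cut-off and its vaccine effectiveness estimate is biased downwards

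*Protocol*

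**What the plan says.** Section 9.8 of the Protocol plans a fuzzy regression discontinuity analysis of influenza-related hospitalisation in 60-69-year-olds, the age band being described as "capturing individuals who are just below (60-64) and just above (65-69) the cutoff". The instrument "will be a binary indicator of whether an individual’s age is ≥ 65 (the vaccination policy cutoff"), and it "is not assumed to directly affect health outcomes other than through vaccination".

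The sample rule is: "Individuals below 65 who are at high-risk will be excluded since they were also offered vaccination". Neither this section nor any other states an exclusion of people with risk conditions at 65-69.

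The same section makes the analysis rest on "similar baseline risk of the influenza outcome in the two age groups" and names as its main assumption that, apart from the jump in uptake, "individuals just below vs. just above 65 should be comparable in terms of health and risk factors". The planned check is to look at covariate distributions near the cut-off. No action is stated if they differ.

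On the running variable, the data to be extracted include "age (in years), and influenza-related hospitalizations for individuals aged 60-69". In section 9.3, Table 6 gives, for the covariate age, "Age defined as 2024 minus birth year".

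**The concern.** Below 65 the sample holds only people without risk conditions. From 65 upwards it holds everyone. The protocol itself says that high-risk groups face more severe influenza complications (section 7), and Table 8 in section 9.8 marks comorbidity as raising the risk of influenza hospitalisation, which is the outcome here. So the sampling rule alone makes baseline risk rise at exactly the age where the vaccine effect is read off.

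A fuzzy design divides the jump in risk by the jump in uptake. An upward jump produced by the sample rule is credited to vaccination and makes the vaccine look weaker, useless or harmful. A narrower bandwidth does not help, because the change in composition sits at the cut-off itself. Inspecting covariates would reveal the break but not repair it.

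At stake is the triangulation in sections 9.8 and 9.9, where supplementary analyses are used to judge bias in the main estimates. A null or negative result produced by the sample rule could be misread as evidence that the cohort VE is confounded.

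**Working it through.** The protocol states no effect size, sample size or power for this analysis, so there is no figure to reproduce. The check applies the fuzzy (Wald) ratio at the cut-off.

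**Inputs from the Protocol**
- Uptake at 65 and over, u1: 75.6% Denmark, 61% Finland, 69% Sweden (section 9.5). These cover all ages from 65, not 65-69 alone.
- Uptake in Danish high-risk people below 65: 29.2% (section 9.5).
- True VE, v: 35.0%, 47% and 61.2%, taken from the studies cited in section 7 (rounded to 35%, 47% and 61% in the thresholds and the 324-cell grid below).

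**Inputs assumed, not in the Protocol**
- High-risk share at 65-69, h: 0.1 to 0.4.
- Relative risk in high-risk people, r: 2, 3 or 5.
- Uptake in low-risk people below 65, u0: 5% to 20%.
- At 65-69, the same uptake and VE in high-risk and other people.

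**Formulas** (risk relative to an unvaccinated low-risk person)
- Above 65, high-risk people kept: Y1 = [1+h(r-1)](1-u1·v).
- Below 65, high-risk people removed: Y0 = 1-u0·v.
- Effect: L = (Y1-Y0)/(u1-u0).
- Apparent VE = -L/(Y0-L·u0), where the denominator is the implied risk without vaccination.
- The sign reverses when h(r-1) exceeds (1-u0·v)/(1-u1·v) - 1.

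**As planned**, v=0.47, u1=0.756, u0=0.10. Here Y0 = 1-0.047 = 0.953, 1-u1·v = 0.6447 and u1-u0 = 0.656.

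| h, r | 1+h(r-1) | Y1 | L | Apparent VE |
|---|---|---|---|---|
| 0.1, 2 | 1.1 | 0.709 | -0.372 | 38% |
| 0.2, 3 | 1.4 | 0.903 | -0.077 | 8% |
| 0.3, 3 | 1.6 | 1.031 | +0.120 | -13% |

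The same three cases at the Finnish uptake of 61% give 33%, -9% and -40%. A vaccine with no effect, at h=0.2, r=3 and uptake 75.6%, gives L = 0.4/0.656 = 0.610 and apparent VE = -0.610/(1-0.061) = -65%.

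**Sign-reversal threshold for h(r-1)**, u0=0.10, at v = 35%, 47%, 61%:
- u1=75.6%: 0.31, 0.48, 0.74
- u1=61%: 0.23, 0.34, 0.50

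Over a grid of three u1, three u0 (5%, 10%, 20%), three v, four h (0.1 to 0.4) and three r, the sign reverses in 182 of 324 cells. In the others VE is attenuated.

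**One rule on both sides**
- High-risk people excluded throughout: h=0 above as well as below, so Y1 = 1-u1·v, L = -v, and apparent VE equals true VE.
- High-risk people kept throughout, with their uptake below 65 set at 29.2%, v=0.47, u1=0.756, u0=0.10: apparent VE is 46% (h=0.1, r=2), 45% (h=0.2, r=3) and 44% (h=0.3, r=3). The uptake jump is 0.64, 0.62 and 0.60, against 0.656 under the first option. The small gap from 47% arises because the formula divides by the average unvaccinated risk rather than that of the people whose vaccination status the cut-off changes.

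**Events lost by excluding on both sides**: high-risk people supply h·r/(1-h+h·r) of the events at 65-69, that is 0.2/1.1 = 18%, 0.6/1.4 = 43% and 0.9/1.6 = 56% in the three cases.

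**The case against.** - **The analysis is supplementary.** The protocol says it will be read alongside the main cohort findings and warns about power, adherence and generalisability. A reader might infer that the main VE results are compromised. They are not: the matched-cohort analysis in section 9.7 does not use this sample. The bias also lowers VE, so it cannot flatter a brand. This stands and limits the severity. The stated cautions do not, however, cover an internal bias built into the sample.

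- **The covariate check would expose the problem.** It probably would, but the protocol attaches no consequence to it.

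- **Reversal of sign is not established.** A reader might infer that the analysis will show harm. The documents do not support that, because h, r and u0 are not given and the outcome depends on the inputs. Take h of 0.15, 0.25 or 0.35, r of 2, 3 or 5, and u0 of 15%. With the cited VE of 61.2% against hospitalisation, the sign reverses in 3, 4 and 5 of these nine cases at uptakes of 75.6%, 69% and 61%. With VE 35% and uptake 61% it reverses in 8 of nine. Only the downward direction is secure.

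- **The running variable.** A reader might also infer that people not yet 65 are wrongly treated as eligible, and that the software is unsuited to age in whole years. The first is not shown. The Table 6 definition is for covariate adjustment and stratification, the discontinuity text says only that age is in years, and the protocol does not say whether eligibility follows exact age or birth year. As to the second, the named R package is offered as one that can be used, not fixed. Whole years give only ten support points across 60-69, which is a fair secondary comment and no more.

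**Conclusion.** The one-sided exclusion is wrong as written. It contradicts the assumptions on which section 9.8 rests the analysis, and it biases the fuzzy VE estimate downwards for any high-risk share above zero and any relative risk above one, given comparable uptake and VE across risk groups at 65-69. The size cannot be fixed from the protocol. Over the assumed range it runs from modest attenuation to a reversed sign.

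This should be corrected before the analysis is run. It is a should-fix rather than a must-fix point, because the damage is confined to one leg of the triangulation.

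**What to change.** Apply one rule on both sides of 65, using the same register-based risk definition, and state what follows if covariates still jump at the cut-off. Either option works:

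- **(a) Exclude on both sides.** Remove everyone aged 60-69 with the defined risk conditions, and describe the estimand as the effect in 60-69-year-olds without risk conditions. In the script this is one filter. The cost is events at 65-69, 18% to 56% in the three worked cases, in an analysis whose power the protocol already questions.
- **(b) Keep on both sides.** Retain high-risk people throughout. The planned fuzzy model already allows for vaccination below the threshold, so having been offered vaccine does not require their removal. The cost is a somewhat smaller uptake jump, 0.60 to 0.64 in the worked cases.

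Optionally, use finer age from date of birth where the registers hold it (Table 7 lists it for Denmark and Finland; for Sweden, Table 6 lists only birth year), or treat age in years as a discrete running variable.
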